#### 5.4.1 Schedule A

- Subjects previously treated with triheptanoin will continue to dose at approximately 35-40% of total daily calories (~1-4g/kg/day, depending on age).
- The visit schedule will be: Visit 1 (day 1), Visit 2 (13 weeks), Visit 3 (26 weeks), Visit 4 (52 weeks), Visit 5 (Year 2, week 26), Visit 6 (Year 2, Week 52), Visit 7 (end of Year 3), Visit 8 (end of Year 4), and Visit 9 (end of Year 5), with telephone follow-up between visits, as needed. (Table 1)

#### 5.4.2 Schedule B

- Subjects who are naïve to triheptanoin will begin a 2-week fixed titration schedule up until they have reached 35-40% of total daily calories (~1-4 g/kg/day depending on age). If a subject has not reached the target of 35-40% of total daily calories, by the end of the 2-week fixed titration period, dose titration should continue until achieved or until the maximally tolerated dose has been established.
- The visit schedule will be Visit 1 (day 1), Phone Visit (2 weeks), Visit 2 (13 weeks), Visit 3 (26 weeks), Visit 4 (52 weeks), Visit 5 (Year 2, week 26), Visit 6 (Year 2, Week 52), Visit 7 (end of Year 3), Visit 8 (end of Year 4), and Visit 9 (end of Year 5), with telephone follow-up between visits, as needed. (Table 2)

#### 5.4.3 Dose Titration Recommendations

The table below is a guide for dose titration of a subject to 35-40% of caloric intake or the maximum tolerated dose if the maximum dose is <35%. Some discretion and flexibility can be used by the Investigator for each subject.

Protocol Number: 2013-NEUR-001  
Version: 4.1  
23-Mar-2018

| Days of Dosing          | Caloric Intake | If Tolerability Issues Arise:   |
|-------------------------|----------------|---|
| Days 1-2                | 10%            | N/A   |
| Days 3-5                | 15%            | N/A   |
| Days 6-8                | 20%            | N/A   |
| Days 9-11               | 25%            | Down-titrate to 20% for 3 more days, then continue to titrate up if possible. |
| Days 12-14              | 30%            | Down-titrate to 20% for 3 more days, then continue to titrate up if possible. |
| Day 15 – study duration | 35-40%         | Down-titrate to 20% for 3 more days, then continue to titrate up if possible. |

*\*Subjects who are unable to tolerate the 35% daily caloric intake will down titrate and re-titrate up to determine tolerability. If a subject is still unable to tolerate the 35% caloric intake, the maximum tolerated dose as determined by the Investigator will be administered for the duration of the study.*

#### 5.4.4 Assessment Schedules

##### 5.4.4.1 Diary

Beginning with the screening visit, subjects or caregivers will record daily seizure frequency and diet in the provided diary for 14 days and then during specified intervals. As such, subjects will record seizures and diet, as applicable, for 14 days post Visit 1 and for 14 days prior to each subsequent study visit.

##### 5.4.4.2 Laboratory

Blood samples will be collected for CBC, Chem-7, ALT/AST, at Screening, Week 13, and every six months through the end of year 2, and annually thereafter for all subjects.

##### 5.4.4.3 Functional Measures

Multiple assessments will be administered at Screening, Months 6 and 12, then once per year thereafter during the initial treatment period for all subjects. Those assessments are:

- The Vineland Adaptive Behavior Scales
- The Barry Albright Scales (BAS)\*
- PedsQL
- Columbia Suicide Severity Rating Scale (C-SSRS)\*

\*The BAS and C-SSRS are the only functional measures that will be completed during the  
Confidential

extension period.

## 6.0 OBSERVATIONS AND MEASUREMENTS

### 6.1 *Vineland Adaptive Behavior Scales, Second Edition (Vineland-II)*.

Vineland-II is an assessment designed to evaluate personal and social skills in individuals from birth to age 90 with two forms, the survey interview form and the parent/caregiver rating form. The two forms are identical except for the mode of administration (either interview or rating scale). Eleven general subdomains are grouped into four domains: communication, daily living skills, socialization, and motor skills. The four domain composite scores then combine to form the adaptive behavior composite for those individuals aged birth to 6 years 11 months. Three domain composite scores (communication, daily living skills and socialization) combine to form the adaptive behavior composite for those aged 7 through 90. Total administration time for the parent/caregiver self-report rating scale is approximately 30-60 minutes.

The Vineland-II Parent/Caregiver rating scales were normed on a representative sample of 3,695 individuals from birth to 90 years. Data for norming and standardization were collected on eleven clinical groups: attention deficit/hyperactivity disorder, autism-nonverbal, autism-verbal, emotional or behavioral disturbance, deafness/hard of hearing, learning disability, cognitively delayed-mild (child and adult samples), cognitively delayed-moderate (child and adult samples), cognitively delayed severe/profound (adult sample) and visual impairment. Extensive analysis of the psychometric properties of the Vineland-II domain, subdomain, and adaptive behavior composite scores have been reported and generally reflect good to excellent reliability and validity (Sparrow et al., 2005). For instance, split half coefficients for the age groups under 3 ranged from .82 to .95 for the Domains and .96 to .98 for the Adaptive Behavior Composite; and from .78 to .92 for the Domains and .90 for the Adaptive Behavior Composite for children between the ages of 6 months and 2 years, 11 months.

### 6.2 *Barry-Albright Dystonia Scale (BAS)*.

The BAS is a 5-point, criterion-based, ordinal scale designed to assess dystonia in eight body regions: eyes, mouth, neck, trunk, upper extremities, and lower extremities. The scale ranges from none (0) to severe (4). The maximum total score is 32. Barry, VanSweringen, and Albright (1999) utilized 10 patients and 17 raters to assess the psychometric properties of the scale. They reported excellent intraclass correlation coefficients (ICC). The reported mean ICC scores were as follows: interrater reliability 0.866, intrarater reliability 0.967 and 0.978, and test-retest reliability 0.978 (before training) and 0.967 (after training).

### 6.3 *The Pediatric Quality of Life Inventory Scale (PedsQL)*.

The PedsQL is a modular approach used to measure the core dimensions of health as defined by the World Health Organization (WHO) as well as role function. The inventory measures health-related quality of life in healthy as well as both acute and chronically ill children. For example, the 23-item Generic Core Scale measures across physical (8 items), social (5 items), school (5 items) and emotional functioning (5 items). It is developmentally age specific utilizing a self-report 5-point Likert scale for ages 8 to 18, and a 3-point scale for the young child. In addition there is a separate module for parents to report for ages 2 to 4 (toddler), 5 to 7 (young child), 8 to 12 (child), and 13 to 18 (adolescent) from the caregiver/parent perspective. It is validated in multi-language form including but not limited to English, Spanish and French.

Items are reverse-scored and linearly transformed to a scale of 0 to 100, such that higher scores indicate better health related quality of life. Internal consistency reliability alpha coefficients for the majority of the child self-report scales and parent proxy-report scales exceeded the minimum reliability standard of .70, with the exception of Self-Report School Functioning at 0.68. The Total Scale Score ( $\alpha = 0.88$  child, 0.90 parent), Physical Health Summary Score ( $\alpha = 0.80$  child, 0.88 parent), and Psychosocial Health Summary Score ( $\alpha = 0.83$  child, 0.86 parent) were acceptable as well.

One-way ANOVA's showing differences among chronically ill, acutely ill, and healthy children for all scales demonstrated construct validity. Multitrait-multimethod analyses revealing correlations with indicators of morbidity and illness burden in the medium to large effect size range demonstrated convergent and divergent validity. Factor analysis resulting in a five-factor solution for self-report and proxy-report supported the conceptualization of the PedsQL as a measurement of an integrated multidimensional construct.

#### 6.4 *Columbia Suicide Severity Rating Scale (C-SSRS)*

The US FDA has recommended the use of the C-CASA as a standardized suicidal rating system for anticonvulsant trials and other centrally acting agents and nonpsychotropic drugs.

The C-SSRS is a suicidality rating scale that is used extensively across primary care, clinical practice, surveillance, research and institutional settings. It is available in 103 languages and maps to the Columbia Classification Algorithm for Suicide Assessment (C-CASA). The C-SSRS was designed to distinguish the domains of suicidal ideation and suicidal behavior using four constructs: severity of ideation, intensity of ideation, behavior, and lethality. Severity of ideation is rated on a 5-point scale with 1 being "wish to be dead", 2 "nonspecific active suicidal thoughts", 3 "suicidal thoughts with methods", 4 "suicidal intent", and 5 "suicidal intent with plan". The intensity of ideation subscale comprises 5 items, each rated on a 5-point scale: frequency, duration, controllability, deterrents, and reason for ideation. The behavior subscale is rated as actual, aborted, and interrupted attempts; preparatory behavior; and nonsuicidal self-injurious behavior. The lethality subscale assesses actual attempts and is

|   |  |
|---|--|
| Protocol Number: 2013-NEUR-001
Version: 4.1
23-Mar-2018 |  |
|---|--|

rated on a 6-point scale. If actual lethality is zero, potential lethality of attempts is rated on a 3-point scale. The C-SSRS has demonstrated good convergent and divergent validity with other multi-informant suicidal ideation and behavior scales. It is highly sensitive and specific for suicidal behavior classifications. Both the ideation and behavior subscales were sensitive to change over time. The intensity of ideation subscale demonstrated moderate to strong internal consistency

The C-SSRS uses different assessment periods, depending on research or clinical need; the lifetime period assesses the worst-point ideation, which research has suggested may be a stronger predictor of subsequent suicide than current ideation. The following versions will be used in this study: (1) baseline, (2) since last visit, (3) pediatric baseline, (4) pediatric since last visit.

Assessments will be administered for subjects ten years of age and older.

## 6.5 Tracking Diary

### 6.5.1 Seizures

A seizure diary will be used to track date, type, number, and unusual presentation of seizures. Subjects will be given a seizure diary at screening to record daily seizure activity for incremental periods of time. They will be instructed to record date and answer the question “Did you/your child experience any seizures today?” An affirmative answer requires completion of the form; a negative answer does not. Regardless of whether a subject experienced a seizure, additional medications administered and not previously recorded will be reported on this daily form. Subjects will describe activity during and post seizure. They will also record the type or description and number of other seizures that occurred that day.

Subjects will complete this form daily during the screening period. They will return the completed diary to the research team at Visit 1. Subjects will then receive a new seizure diary. Subjects will track daily seizures for two weeks following Visit one and then for two weeks prior to each subsequent study visit. Subjects will return the completed diary and receive a new diary at each visit.

### 6.5.2 Diet

A diet diary will be used to track daily food consumption. Subjects will record the time of consumption, type of food or beverage, amount eaten, place eaten, and individuals present at time of consumption. This should be completed for each of the three days prior to a study visit. The form is incorporated into the seizure diary. Thus, a grid entitled Diet Diary is located below the seizure diary for each of the final days before a study visit.

## 7.0 CRITERIA FOR EVALUATION

### 7.1 *Safety*

Safety events and tolerability will be recorded as adverse events (AE) or serious adverse events (SAE) except for those events that are related to GLUT1 deficiency such as epileptic seizures or abnormal movements.

Physical examination, weight, vital signs, and laboratory tests will be conducted periodically

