## **An Open-Label Trial of Triheptanoin in Patients with Glucose Transporter Type-1 Deficiency Syndrome (GLUT1 DS)**

### **1.0 GOALS AND OBJECTIVES**

- 1.1 The primary objective of the study is:
- To evaluate the safety of triheptanoin via adverse event rates and laboratory values.
- 1.2 The secondary objective of the study is:
- To evaluate the long-term efficacy of triheptanoin as measured by the change in seizure frequency from historical baseline.

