#### *10.6 Adverse Event Reporting*

##### 10.6.1 Safety monitoring

|   |  |
|---|--|
| Protocol Number: 2013-NEUR-001
Version: 4.1
23-Mar-2018 |  |
|---|--|

Safety monitoring includes the systematic review of clinical laboratory results and measurement data for trends that may impact patient safety. The processing, reviewing, and reporting of adverse experiences and serious AE are also captured.

- A serious adverse event (SAE) is defined as: Death, or immediately life-threatening, or permanently [or significantly] disabling, or requiring hospitalization, or prolongation of hospitalization, or a congenital anomaly. Elective planned hospitalizations, unrelated to either the disease being studied or the study (e.g., for tonsillectomy), will not be considered serious adverse events.
- An unexpected adverse event is one that is not identified in nature, severity or frequency as described in for these AEDs.

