#### 10.6.3 Stopping Rules

The Medical Safety Monitor will act in an advisory capacity to monitor the safety of subjects on a routine basis throughout the trial. The drug safety and pharmacovigilance group at Ultragenyx will review SAEs and may provide advice in any determination of whether study enrollment should be paused or if the study should be halted.

Individual subjects who experience any unexpected and possibly, probably, or definitely drug-related SAEs that represent a change in the nature or an increase in frequency of the serious event from their prior medical history will be assessed as to whether the subject will continue on the study.

Should unexpected and possibly, probably, or definitely drug-related SAEs occur, a full clinical evaluation will be performed by the medical safety monitor, the principal investigator, and drug safety and pharmacovigilance group in order to make a decision regarding what actions to take, including whether to recommend stopping the study and informing the IRB.

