#### 10.6.4 Safety Report

Copies of all reports will be stored in the Study File. All SAEs will be reported to the FDA, the CCHCS IRB, and the supporting institution, Ultragenyx, Inc.

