### 11.0 STATISTICAL CONSIDERATIONS

#### 11.1 *Safety Analysis*

Safety data will be reviewed annually or more frequently, as needed, by another physician investigator familiar with the disorder and treatment. For the safety analysis, the numbers (frequency) and incidence rates of AEs and SAEs will be summarized during exposure to triheptanoin throughout the study. The analyses of safety will include all subjects who receive any triheptanoin during the study and provide any post-treatment safety information. All AEs will be coded using the Medical Dictionary for Regulatory Activities (MedDRA). The incidence and frequency of AEs will be summarized by System Organ Class (SOC), Preferred Term (PT), relationship to study drug, and severity. A by-subject listing will be provided for those subjects who experience a SAE, including death, or experience an AE associated with early withdrawal from the study or study drug treatment.

Clinical laboratory data will be summarized by the type of laboratory test. The frequency and percentage of subjects who experience abnormal clinical laboratory results (i.e., outside of reference ranges) and/or clinically significant abnormalities after study drug administration will be presented for each clinical laboratory measurement. For each clinical laboratory measurement, descriptive statistics will be provided for Baseline and all subsequent scheduled visits during which laboratory measurements were obtained. Changes from Baseline to the treatment visits will also be provided. Descriptive statistics of vital signs and concomitant medications will be provided in a similar manner.

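### Section 7.1 exempts GLUT1-related events from AE and SAE recording with no limit by seriousness or worsening, which conflicts with the SAE definition in 10.6.1 and, if followed, removes such events from the primary safety rates

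*Combined protocol and SAP*

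**What the plan says.** The primary objective in section 1.1 is "To evaluate the safety of triheptanoin via adverse event rates and laboratory values". Section 11.1 puts this into effect: "the numbers (frequency) and incidence rates of AEs and SAEs will be summarized during exposure to triheptanoin throughout the study".

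Section 7.1 sets the recording rule. Safety and tolerability events are entered as AEs or SAEs "except for those events that are related to GLUT1 deficiency such as epileptic seizures or abnormal movements". The exception covers both categories. It contains no condition on severity, seriousness, change from the subject's usual pattern, or possible relation to the drug.

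Section 10.6.1 defines an SAE by outcome: "Death, or immediately life-threatening, or permanently [or significantly] disabling, or requiring hospitalization, or prolongation of hospitalization, or a congenital anomaly". Its single exclusion is "Elective planned hospitalizations, unrelated to either the disease being studied or the study". It has no exclusion for events of the disease itself and does not refer to 7.1.

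Three later provisions depend on what has been recorded:
- Section 10.6.3 calls for a decision on continuing in the study for subjects with "unexpected and possibly, probably, or definitely drug-related SAEs that represent a change in the nature or an increase in frequency of the serious event", compared with their own history.
- Section 10.6.4 (Safety Report) states: "All SAEs will be reported to the FDA, the CCHCS IRB, and the supporting institution".
- Section 11.1 states: "A by-subject listing will be provided for those subjects who experience a SAE, including death, or experience an AE associated with early withdrawal".

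None of the three makes an exception for disease-related events.

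**The concern.** Seizures and movement disorder are the main features of GLUT1 DS (section 2.1), so 7.1 exempts the kind of serious event this population is prone to. Some exemption is sensible: seizures are the efficacy outcome, and entering each habitual seizure as an AE would swamp the tables. The difficulty is that this exemption has no boundary. It treats an admission for status epilepticus, or a clear worsening on treatment, in the same way as a typical baseline seizure.

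At stake is the primary output of a study with no control arm. The reported AE and SAE rates have to stand on their own, and a rule that keeps a class of serious events out of the numerator makes them look better than they are. The same rule would also affect what reaches the FDA, the IRB and the supporting company.

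**Working it through.** The plan gives no figure on this point to reproduce. The check is mainly a comparison of text.

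**1. One test case under both rules.** Take an unplanned hospital admission for seizures.
- Section 7.1: a seizure is one of the two named examples, so the event is neither an AE nor an SAE.
- Section 10.6.1: the event required hospitalization, so it is an SAE. The exclusion does not apply, because the admission is neither elective nor planned, nor unrelated to the disease.

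The same event is classified in two ways, and no section states an order of precedence.

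**2. Consequence of each reading.**
- If 7.1 filters events before 10.6.1 is applied, the admission is absent from the SAE rate, the by-subject listing and the SAE reports.
- If 10.6.1 governs, 7.1 is wrong for SAEs. New or worsened non-serious events still go unrecorded as AEs. A subject who left because of them would then have no AE to trigger the early-withdrawal part of the listing.

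**3. Effect on the 10.6.3 review.** That review needs an SAE that is unexpected and at least possibly drug-related.
- An event attributed wholly to the disease would not qualify, whatever 7.1 says.
- An event attributed to the drug can be argued to lie outside the 7.1 exemption.
- An event attributed to the disease but also possibly to the drug could be exempted under 7.1 and so miss the review.

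Only this last group is affected.

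**4. Direction.** Section 11.1 includes subjects who took any triheptanoin and have any safety information after treatment. Exempting a particular event does not add to or reduce that denominator. The exemption can only take events out of the numerator, so the rates can only fall.

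**5. Scale per subject.** SAE incidence = subjects with at least one SAE / N. Removing a subject whose only SAE is exempted changes it by 1/N:
- N = 50 (maximum in section 3.2): 1/50 = 2.0 percentage points
- N = 30 (assumed): 1/30 = 3.3 points
- N = 20 (assumed): 1/20 = 5.0 points

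This would be true of any unrecorded event in any trial. It shows the unit of effect and does not estimate the loss.

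**6. Whether other data replace the record.** Section 6.5.1 has the diary capture the date, type and number of seizures, anything unusual about them, what happened during and after, and additional medication. Sections 5.4.1 and 5.4.4.1 place it in 14-day windows, one after Visit 1 and one before each of Visits 2 to 9: 14 + 8 × 14 = 126 days. Five years is 5 × 365.25 = 1,826 days, so the windows cover 126 / 1,826 = 6.9% of treatment time. No seriousness or admission field is described, and nothing carries diary entries into the AE or SAE tables. Section 11.2 uses seizure data only for the comparison of monthly frequency with the historical rate and the median percent reduction. Barry-Albright scores are collected (section 5.4.4.3), but section 11 plans no analysis of them.

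**The case against.** The best defence is that 7.1 is a specific exception beside a general definition, which is an ordinary structure, and that its causal wording protects it: it exempts events related to GLUT1 deficiency, so a seizure caused by the drug is not exempt. On this view 10.6.3, by speaking of change from a subject's history, shows that worsened serious events were meant to be captured.

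Part of this stands. Section 10.6.3 does suggest that a narrower rule was intended. But 7.1 names seizures and abnormal movements as a class and gives no rule for attribution, and 10.6.1 has its own, narrower exclusion. The apparent intent of 10.6.3 therefore adds to the conflict. Section 2.2.2 also describes many SAEs in earlier triheptanoin subjects as consistent with their underlying disease, so disease-type events were counted as SAEs in that experience.

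A reader might infer more than the documents support:
- *That serious seizures would go unseen.* AE review at every visit and at termination, the diary, trend review and at least annual physician review may all detect worsening. The gap lies in the AE and SAE tables and reports.
- *That a seizure death would certainly be left out.* Sections 10.6.1 and 11.1 both name death. Its omission follows only on the widest reading of 7.1.
- *That the 10.6.3 review is disabled.* Only events of mixed attribution are affected.
- *That the efficacy summary could never show worsening.* Section 11.2 also compares monthly frequency with the historical rate, and a median moves when its middle values move. A median's insensitivity to its lower tail is a general property and says nothing specific about 7.1.

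The monitoring charter, the local IRB policy and the Data Dictionary are not available and may hold a recording rule. Such a rule would help in practice but would not remove the contradiction within the protocol.

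**Conclusion.** Wrong as written. Sections 7.1 and 10.6.1 classify the same serious event differently, and no text resolves it. Followed literally, 7.1 leaves serious or worsened seizure and movement events out of the primary AE and SAE rates, the by-subject listing and SAE reporting. The bias has a known direction, towards lower reported rates.

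Its size is unknown: the documents give no rate of serious seizures or movement events, so no number of lost events is claimed. The per-subject effect of 2.0 percentage points assumes 50 subjects in the safety analysis and a subject with no other SAE. The conclusion rests on the protocol text alone and assumes that sites would apply 7.1 as it is worded.

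**What to change.** 1. Reconcile 7.1 with 10.6.1 and 10.6.3, and state which section governs recording. Limit the 7.1 exception to non-serious GLUT1-related events consistent with the subject's documented baseline. Any event meeting 10.6.1 is then recorded as an SAE, and new or worsened events are recorded as AEs.
2. In 11.1, tabulate disease-related AEs and SAEs separately, so that the rates can be read with and without them.

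The cost is a short amendment to 7.1 and 11.1, guidance for completing the eCRF and one extra table. The downside is more AE and SAE entries and slightly less favourable rates; the separate table lets a reader see how much of that comes from the disease category.
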